17.3 Analysis data sets

17.3.1 Full analysis set

The FAS will consist of all subjects who have been randomized and received at least one dose of IMP.

17.3.2 Per protocol analysis

The PP population will consist of all subjects who have been randomized, completed the study period and without any major protocol violations. All violations will be presented and discussed at the clean file meeting.

The baseline and safety data will be presented using the FAS population. All data regarding extraction of nicotine will use the PP population.

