10.7.1 Subject replacement

Subjects who are prematurely withdrawn from the study for any reason will not be replaced.

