12.5.3 Collection of pouches and analysis

Pouches for the determination of nicotine after administration of the Investigational Product will be collected after 60 minutes (see Overall study design and schedule of events in Section 9.1). The following time window will apply for the pouch sampling:

 $- \pm 1$ min.

- The date and time of collection of each pouch will be recorded in the CRF.

All the collected pouches will be collected and frozen immediately at -20°C.

Pouches for extraction of nicotine will be analyzed by Swedish Match. Pouches from all evaluable subjects excluding withdrawn or dropout subjects will be analyzed.

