13.2 Nicotine extraction

13.2.1 Sample collection

The nicotine content per portion of used and unused pouches, respectively, will be estimated. Each used pouch is collected and frozen (-20°C) pending analysis of nicotine. Frozen samples of used pouches collected for nicotine determinations will be shipped to Swedish Match laboratories.

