17.1 General

Continuous data will be presented using summary statistics. Data will be presented in terms of number (N), arithmetic mean, standard deviation (SD), minimum and maximum value.

Categorical data will be presented as counts and percentages. When applicable, summary data will be presented by treatment, and by assessment time. Individual subject data will be listed by subject number, treatment, and, where applicable, by assessment time.

A significance level of 5% with two-sided tests will be used in all comparisons.

The test articles below will in all analyses be compared to the reference product.

Any comparisons between the test articles will be described in the SAP.

Test articles:

1= ZYN Smooth containing 3 mg nicotine per portion

2= ZYN Smooth containing 6 mg nicotine per portion

3= ZYN Smooth containing 3 mg nicotine per portion (alternative manufacturing process)

4= ZYN Smooth containing 6 mg nicotine per portion (alternative manufacturing process)

Reference articles:

5= Swedish portion snus PSWL 1.0 g (8 mg nicotine/g)

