17.6 Analysis of secondary endpoints

The mean + SD extracted dose of nicotine from each pouch, will be calculated. The extracted dose of nicotine will be analyzed using the signed Wilcoxon rank sum test and Students t-test for within subject difference. The correlation between the AUC and the total amount of nicotine extracted from the pouch will be analyzed using Proc corr. in SAS.

The mean + SD of AUCinf based on plasma concentrations of nicotine after administration of of each pouch, will be calculated. AUC60min, Cmax, Tmax, AUCo-t and terminal half-life will also be calculated.

AUC60min, Cmax, Tmax, AUCo-t and terminal half-life of a novel, non-tobacco-based nicotine pouch to that of a Swedish snus pouch will be described using summary statistics and analyzed using signed Wilcoxon rank sum test for within subject difference.

Pulse rate and VAS for measure of subjective "head buzz" (head rush, "hit", feeling alert, overall "product strength"), will be summarized by treatment and period using descriptive statistics.

The intra subject difference of pulse rate will be analyzed using the signed Wilcoxon rank sum test and Students t-test for within subject difference.

The intra subject difference of VAS scales for "head buzz" (head rush, "hit", feeling alert, overall "product strength") will be analyzed using the signed Wilcoxon rank sum test and Students t-test for within subject difference.

All AE data will be fully listed by Investigator terms and MedDRA Preferred Term (PT). AE data will be summarized by System Organ Class (SOC) and PT.

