17.7.2 Handling of dropouts or missing data

Missing data will not be imputed.

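### Nicotine extraction is analysed only in study completers, and withdrawn subjects' pouches go unassayed, so valid product-versus-snus pairs are discarded: a cheap improvement

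*Protocol*

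**What the plan says.** The protocol fixes three rules that act together.

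- Section 17.3.2 defines the per-protocol set: "The PP population will consist of all subjects who have been randomized, completed the study period and without any major protocol violations". It then says: "All data regarding extraction of nicotine will use the PP population".
- Section 12.5.3, on the pouch assay, says: "Pouches from all evaluable subjects excluding withdrawn or dropout subjects will be analyzed".
- The section on subject replacement (numbered 10.7.1, after 10.7.2) says: "Subjects who are prematurely withdrawn from the study for any reason will not be replaced".

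The analysis these rules feed is pairwise. Section 17.1 says: "The test articles below will in all analyses be compared to the reference product". Section 17.6 says: "The extracted dose of nicotine will be analyzed using the signed Wilcoxon rank sum test and Students t-test for within subject difference". Section 17.7.2 adds: "Missing data will not be imputed".

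The material itself exists. Section 13.2.1 says: "Each used pouch is collected and frozen (-20°C) pending analysis of nicotine".

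Extraction is listed as secondary in sections 8.2 and 8.2.1 and is analysed as such in 17.6, but section 17.2 calls it the primary endpoint and bases the sample size on it.

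**The concern.** A paired comparison of one ZYN product with snus needs that subject's ZYN period and snus period and nothing else. A subject who completes snus and three ZYN products and then withdraws has three complete pairs. Under 17.3.2 that subject leaves all four comparisons, and under 12.5.3 the pouches already in the freezer are not assayed. These are stated rules, not details left open for the SAP. If the assay rule is followed, a SAP that widens the analysis set would find no extraction values for these subjects.

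At stake is mainly precision, in a trial that enrols 18 against a calculated need of 16 and does not replace losses. There is a secondary risk of selection. The study is open, and section 12.6.1.1 lists nausea, vomiting and palpitations among suspected reactions. If withdrawal is related to how a product is tolerated, dropping a withdrawn subject's completed periods selects on tolerability.

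**Working it through.** **Inputs from the protocol.** Five-way cross-over with 18 subjects (9.1); four test articles, each against snus, two-sided 5% (17.1); snus extraction 2.18 mg, complete extraction assumed for ZYN, SD 5.0, n = 16, power 80% (17.2).

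**Assumptions, because the protocol gives no dropout rate.** Withdrawal is permanent. Every subject takes period 1 and then withdraws with probability h before each of periods 2 to 5. Order is balanced. Section 17.2 specifies Latin squares, but 18 is not a multiple of 5, so the balance is approximate.

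**Step 1: reproduce the plan's n.** For the 6 mg contrast the difference is 6 − 2.18 = 3.82 mg. Taking 5.0 as the SD of within-subject differences, a paired t-test (noncentral t with n − 1 degrees of freedom and noncentrality 3.82/5.0 × √n) gives:

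| n | 18 | 17 | 16 | 15 | 14 |
|---|---|---|---|---|---|
| Power, 6 mg | 86.3% | 84.0% | 81.5% | 78.6% | 75.3% |

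The smallest n reaching 80% is 16, as stated. For the 3 mg contrast the difference is 3 − 2.18 = 0.82 mg, and power at n = 14 to 16 is only about 9%.

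**Step 2: pairs held by a subject who stops after m periods.** A given test-snus pair is complete if both products fall in the first m of five positions. The probability is (m/5) × ((m − 1)/4) = m(m − 1)/20.

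| Periods completed, m | 2 | 3 | 4 | 5 |
|---|---|---|---|---|
| P(given pair complete) | 0.1 | 0.3 | 0.6 | 1.0 |
| Expected pairs out of 4 | 0.4 | 1.2 | 2.4 | 4.0 |

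The plan uses none of the pairs for m below 5. A subject who stops after period 1, or before reaching snus, has no pair to lose.

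**Step 3: completers against available pairs.** The proportion completing is (1 − h)^4. The proportion stopping after m = 1 to 4 periods is h(1 − h)^(m − 1). The proportion with a given pair is the sum of these weighted by m(m − 1)/20.

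For h = 0.05, completers: 18 × 0.95^4 = 18 × 0.8145 = 14.7. Available pairs: 18 × (0.8145 + 0.6 × 0.0429 + 0.3 × 0.0451 + 0.1 × 0.0475) = 18 × 0.8585 = 15.5.

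| Assumed h | Completers | Pairs per contrast | Gain |
|---|---|---|---|
| 2% | 16.6 | 16.9 | 0.3 |
| 5% | 14.7 | 15.5 | 0.8 |
| 10% | 11.8 | 13.2 | 1.4 |

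**Step 4: what the gain is worth.** At h = 5% the gain is 0.8 of a subject. Between n = 15 and n = 16 power for the 6 mg contrast rises by 81.5 − 78.6 = 2.9 points, so the gain is about 0.8 × 2.9 = 2.3 points, or roughly 2 to 3.

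**Step 5: late withdrawals.** If 1, 2, 3 or 4 subjects leave after period 4, completers number 17, 16, 15 or 14. Expected pairs per contrast are 18 − k + 0.6k = 17.6, 17.2, 16.8 or 16.4. With three such losses the completer analysis falls below 80% power on the plan's inputs, while the available pairs still exceed 16.

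**The case against.** The best reply is that this is a modest efficiency point on an endpoint that section 8 lists as secondary, and that a completer per-protocol set is a familiar choice. Much of that stands. The effect is nil without withdrawals and small with one or two. The 3 mg contrasts have about 9% power on the plan's inputs either way. If the SD of differences were well below 5.0 (say 2.0 to 2.5, an assumption), 6 mg power would be about 99.9% or more even at n = 13, and the lost pairs would hardly matter for that test.

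A reader might infer four stronger things that the document does not support.

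- *A larger loss.* Treating visits as missed independently at 5% gives 18 × 0.95^5 = 13.9 completers against 18 × 0.95^2 = 16.2 pairs, a gap of 2.3. But the assay and replacement rules concern withdrawal and dropout, after which all later visits are lost. The gap is then 0.8.
- *That the fix restores planned power.* A fall from 81.5% at 16 to 75.3% at 14 is mostly dropout itself, which no choice of analysis set can undo.
- *That the data are irretrievable.* The used pouches are frozen, and the disposal rule in section 13.1.1 covers plasma samples. Late assay may be possible; the plan simply does not provide for it.
- *That leaving AUCinf, pulse rate and VAS without an analysis set is an error.* Section 17 calls itself an outline and defers detail to a SAP, where that allocation can properly be made.

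It can also be said that section 17.3.2 does not literally require five periods. In a five-way cross-over, alongside a rule excluding withdrawn subjects' pouches, no other reading is natural.

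**Conclusion.** The point holds as a cheap improvement. Sections 17.3.2 and 12.5.3 as written discard complete test-snus pairs that the planned paired tests could use. Under permanent withdrawal at an assumed 2% to 10% hazard before each later period, the loss is about 0.3 to 1.4 pairs per contrast. At 5% that is about 2 to 3 points of power for the 6 mg contrast, given the plan's difference of 3.82 mg and SD of 5.0. The size depends on a dropout rate that the protocol does not state.

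The selection argument is secondary and unquantified. Available pairs reduce selection on tolerability but do not remove it, because the periods never taken stay missing.

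**What to change.** Amend section 12.5.3 so that every collected used pouch is assayed, whether or not the subject later withdraws. Amend section 17.3.2 so that each extraction contrast uses all subjects with evaluable data for the two periods concerned, and the AUC-extraction correlation uses all periods with both measurements evaluable. Exclude only periods with a violation that affects the measurement in question. Keep the completer per-protocol set as a sensitivity analysis. The planned Wilcoxon and t-tests need no change.

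The cost is two wording changes, a few extra assays of pouches already frozen, and slightly different numbers of subjects per contrast, which should be reported with each result. The assay wording should change before the pouches are analysed.

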17.4 Description of study population

17.4.1 Demographics and baseline characteristics

Descriptive statistics for demographics, weight and height will be presented by dose group.

17.4.2 Medical/surgical history and prior/concomitant medication

Medical/surgical history and prior/concomitant medications will be presented by descriptive statistics by dose group.

17.4.3 Treatment compliance

The number of subjects treated in each by dose group will be tabulated.

17.5 Analysis of primary endpoint

AUC_{inf} based on plasma concentrations of nicotine after administration of one single dose of a novel, non-tobacco-based nicotine pouch containing 3 and 6 mg of nicotine, to that of one single dose from a 1 g Swedish snus pouch containing 8 mg of nicotine will be described using summary statistics and non-parametric signed Wilcoxon rank sum test for within subject difference.

17.6 Analysis of secondary endpoints

The mean + SD extracted dose of nicotine from each pouch, will be calculated. The extracted dose of nicotine will be analyzed using the signed Wilcoxon rank sum test and Students t-test for within subject difference. The correlation between the AUC and the total amount of nicotine extracted from the pouch will be analyzed using Proc corr. in SAS.

The mean + SD of AUCinf based on plasma concentrations of nicotine after administration of of each pouch, will be calculated. AUC60min, Cmax, Tmax, AUCo-t and terminal half-life will also be calculated.

AUC60min, Cmax, Tmax, AUCo-t and terminal half-life of a novel, non-tobacco-based nicotine pouch to that of a Swedish snus pouch will be described using summary statistics and analyzed using signed Wilcoxon rank sum test for within subject difference.

Pulse rate and VAS for measure of subjective "head buzz" (head rush, "hit", feeling alert, overall "product strength"), will be summarized by treatment and period using descriptive statistics.

The intra subject difference of pulse rate will be analyzed using the signed Wilcoxon rank sum test and Students t-test for within subject difference.

The intra subject difference of VAS scales for "head buzz" (head rush, "hit", feeling alert, overall "product strength") will be analyzed using the signed Wilcoxon rank sum test and Students t-test for within subject difference.

All AE data will be fully listed by Investigator terms and MedDRA Preferred Term (PT). AE data will be summarized by System Organ Class (SOC) and PT.

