7 INTRODUCTION

7.1 Project background

Sweden displays the lowest prevalence of smoking in Europe, particularly among males. Population surveys have indicated that snus is the most frequently used smoking cessation aid. Snus is sometimes used as a last resort for people who have failed stopping smoking with the available, pharmaceutical smoking cessation aids. Smokeless tobacco is capable of rapidly delivering nicotine to the bloodstream (Fant et al 1999), and therefore may be more satisfactory among smokers than currently available pharmaceutical nicotine products. Traditionally there has been no non-tobacco-based nicotine product on the Swedish market intended for recreational use similar to Swedish snus. Despite the vast risk differential between snus and cigarettes in terms of adverse long-term health effects including cancer, cardiovascular disease and chronic lung disease, snus remains a controversial product as it contains tobacco and is intended for recreational use. The tobacco component of snus explains why it contains measurable amounts of hazardous constituents such as potentially carcinogenic nitrosamines, albeit at very low concentrations.

Recently, a novel, non-tobacco-based nicotine product (ZYN®) has been developed. It has some features that are similar to snus: it comes in pouches with a nicotine content of 3 or 6 mg; it is used the same way as snus, that is, it is placed under the upper lip. In contrast to snus the product contains no nitrosamines or polycyclic hydrocarbons (PAHs), which are the two main classes of unwanted substances in snus that are classified as potentially carcinogenic. Other unwanted substances in ZYN® are present in comparable or lower concentrations than in snus. The toxicological safety profile of ZYN® thus represents a significant improvement over snus with the exception of the nicotine content which is only marginally lower than in snus (3 or 6 mg in ZYN® versus e g 8-12 mg in a conventional 1.0 g snus pouch).

Commercially available snus products have a nicotine content ranging between 1-2%. Previous studies (Lunell E and Curvall M 2011), have indicated that on average about 15-20% of the total nicotine content is extracted and absorbed, with large inter-individual variation. Extraction is generally not linear with pouch size: surface area, saliva penetration and diffusion factors may be important determinants of nicotine uptake.

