8.2 Secondary objectives

- 1. To compare AUC_{60min} , C_{max} , T_{max} , AUCo-t and terminal half-life of a novel, non-tobacco-based nicotine pouch to that of a Swedish snus pouch.
- 2. To compare the estimated *in-vivo* extracted amount of nicotine from a novel, non-tobacco-based nicotine pouch containing 3 and 6 mg of nicotine, respectively, with that from a 1 g Swedish snus pouch containing 8 mg of nicotine.
- **3.** Comparison of pulse rate and subjective effects ("head buzz") after study product administration (proxy for *in vivo* nicotine uptake).
- 4. Adverse events
- 8.2.1 Secondary endpoints
 - 1. AUC_{60min}, C_{max}, T_{max}, AUCo-t and terminal half-life of a novel, non-tobacco-based nicotine pouch to that of a Swedish snus pouch.
 - 2. In-vivo extracted amount of nicotine
 - 3. To assess the correlation between the estimates of AUC(inf) and the total amount of nicotine extracted from the ZYN® pouches.
 - 4. Pulse rate and VAS for measure "head buzz" (head rush, "hit", feeling alert, overall "product strength"), using a 100-mm visual analogue scale (VAS) anchored with "not at all" to "extremely" at preset time points up to 60 minutes (predose, + 5min, +10 min, +15 min, +30 min, +60 min after each dose), respectively, after study product administration (proxy for systemic uptake).
 - 5. Collection of adverse events

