9 INVESTIGATIONAL PLAN

9.1 Overall study design and schedule of events

The study will be conducted as an open, randomized, five-way cross-over, single dose administration. The study will include 18 subjects.

The subjects included will be healthy males and females aged ≥ 19 years who use tobaccobased snus, since ≥ 1 year with a weekly consumption of three or more snus cans (brands with nicotine content $\leq 1\%$) or two or more cans (brands with nicotine content $\geq 1\%$). Subjects who are pregnant or who have a history of hypertension or any cardiovascular disease are excluded. Subjects shall be abstinent from snus and all other nicotine containing products from 8.00 p.m. the night before each trial day.

Before entry to the study subjects undergo screening evaluations including smoking and snus use, medical history and pulse rate measurements before/after application of their usual brand of snus. The puls rate assessment will be made in abstinent condition from 8 p.m. the night before.

A pulse rate increase of ≥ 10 beats/min in the morning before use of any nicotine containing product will classify the subject as eligible for participation the study.

Subjects report to the clinic on separate days for the 5 experimental sessions. The subjects are instructed to abstain from snus, cigarettes or other nicotine delivery products as from 8 pm the evening before. All sessions are performed during the morning hours to facilitate abstinence. The subjects should certify abstinence before each treatment is started.

The treatments are administered as single doses in a pre-determined randomized order. The subject keeps the pouch still between the upper lip and the gum for 60 minutes and are instructed not to manipulate the pouch with the tongue or lips. The subjects are instructed not to eat, drink, chew chewing gum or brush teeth from 30 minutes before application of treatment, during application of investigational products and 30 minutes after the investigational product have been taken out. [5].

Each used pouch is collected and frozen (-20°C) pending analyses of nicotine.

Assessment	Screening	Cross-over phase	Follow-up Phone contact
	Visit 1 ¹	Visit 2-6 ²	Visit 7
	Day -14 to -1	Day 1 followed by 1-14 day(s) of wash-out. Repeated for each dose time point	7 Days after last dose – 3/+7 days
Informed consent	Х		
Eligibility	Х	X ⁸	
Demographics	Х		
Prior and Concomitant medication	Х	X	X
Medical history	Х		
Urine pregnancy test ³	Х		

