17.2 Determination of sample size

The primary endpoint is nicotine extraction. The study will include 18 subjects. A previous study [Lunell E & Curvall M 2011] has made the calculation of sample size possible. Nicotine extraction from a 1 g Swedish portion snus (PSWL) containing 8mg nicotine/pouch was estimated at 2.18 ± 0.92 mg per portion. Under the assumption of a complete dissolution and *in-vivo* extraction of the 3 and 6 mg ZYN® products, respectively, versus the 2.18 ± 0.92 mg nicotine, and a standard deviation of 5.0 the estimated sample size is 16 with a power of 80% and alpha=0.05. The randomization will be performed using Latin Squares approach.

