17.7 Statistical/analytical issues

17.7.1 Adjustments for covariates

No adjustments for covariates will be performed.

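### The planned correlation of AUCinf with extracted nicotine most naturally pools 3 mg and 6 mg ZYN pouches and repeated subjects, so it would largely reflect the strength contrast

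*Protocol*

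**What the plan says.** Section 8.2.1, item 3, defines the secondary endpoint: "To assess the correlation between the estimates of AUC(inf) and the total amount of nicotine extracted from the ZYN® pouches". One correlation is named, and neither strength nor product is separated.

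Section 17.6 gives the method: "The correlation between the AUC and the total amount of nicotine extracted from the pouch will be analyzed using Proc corr. in SAS". This sentence does not repeat the restriction to ZYN. It also does not say which AUC is meant, although the protocol uses AUCinf, AUC60min and AUC0-t.

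Section 17.7.1 adds: "No adjustments for covariates will be performed".

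On the data structure, section 9.1 states: "The study will be conducted as an open, randomized, five-way cross-over, single dose administration". Section 11.1 lists four ZYN products, two of 3 mg and two of 6 mg, plus snus. Section 17.2 states: "The study will include 18 subjects". Section 17 calls itself an outline and leaves detail to a separate SAP.

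**The concern.** Nominal strength can be expected to raise both variables. A 6 mg pouch has more nicotine to release than a 3 mg pouch and probably gives a higher AUC. A coefficient taken across both strengths therefore picks up the strength contrast, even if a subject who extracts more from a given pouch has no higher AUC than one who extracts less.

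In addition, the default p-value from Proc corr treats every pair as independent, whereas each subject contributes up to four.

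This correlation is the only listed endpoint that links extraction to systemic uptake, a link that section 7.1 places within the main aim of the study. If pooled, the reported coefficient could be taken as evidence that individual extraction predicts individual uptake when it mainly shows that the stronger pouch delivers more.

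**Working it through.** **Plan's own figure.** The protocol states no size, power or threshold for the correlation. Its only computed design figure, 16 subjects in section 17.2, can be reproduced with a two-sided paired t-test (difference 6 − 2.18 = 3.82 mg, SD 5.0, power 80%, alpha 0.05). It has no bearing on this endpoint.

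**Inputs from the protocol.**
- 18 subjects × 4 ZYN products = up to 72 pairs.
- Strengths: "it comes in pouches with a nicotine content of 3 or 6 mg" (section 7.1).
- Test level: "A significance level of 5% with two-sided tests will be used in all comparisons" (section 17.1).
- The only extraction spread given is for snus, which "was estimated at 2.18 ± 0.92 mg per portion" (section 17.2). Its CV is 0.92/2.18 = 0.42, used here as the upper end.

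**Assumed inputs (not in the protocol).** Extraction CV 0.10 to 0.42; AUC CV 0.3 to 0.6; the same mean fraction extracted from both strengths (extraction ratio 2); 6:3 mg AUC ratio 1.25 to 2.0; subject share of log-variance 0.5 for extraction and 0.7 for AUC; no association within a product.

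**Step 1, strength mixing by hand.** With half the pairs at each strength and a mean ratio R, the between-strength variance is b = (R − 1)²/4 and the within-strength variance is w = CV²(1 + R²)/2, in units of the squared 3 mg mean. With no association within a product, pooled r ≈ √[b/(b+w)] for extraction times the same term for AUC.

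Example with extraction CV 0.20, AUC CV 0.4 and both ratios 2:
- extraction: √[0.25/(0.25 + 0.10)] = 0.845
- AUC: √[0.25/(0.25 + 0.40)] = 0.620
- product: r ≈ 0.52

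With 72 pairs, p<0.05 needs |r| > 1.994/√(70 + 1.994²) = 0.23.

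**Step 2, simulation** (4,000 trials per setting, log-normal variables, naive Pearson test on 72 pairs).

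| Extraction CV | AUC CV | AUC ratio 6:3 mg | r by hand | Median r | p<0.05 | p<0.001 |
|---|---|---|---|---|---|---|
| 0.10 | 0.3 | 2.0 | 0.69 | 0.71 | 100% | 100% |
| 0.20 | 0.4 | 2.0 | 0.52 | 0.55 | 99.95% | 96% |
| 0.42 | 0.6 | 2.0 | 0.28 | 0.31 | 70% | 30% |
| 0.20 | 0.3 | 1.5 | 0.46 | 0.49 | 99% | 85% |
| 0.42 | 0.6 | 1.5 | 0.19 | 0.20 | 42% | 10% |
| 0.10 | 0.3 | 1.25 | 0.33 | 0.35 | 92% | 33% |
| 0.42 | 0.6 | 1.25 | 0.11 | 0.12 | 22% | 3% |

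**Step 3, repeated subjects alone.** With no strength mixing, k pairs per subject and intra-subject correlation ρ in both variables, the variance of r grows by about 1 + (k − 1)ρ². The actual error of a nominal 5% test is then about 2Φ(−1.96/√[1 + (k − 1)ρ²]).
- k = 4 and ρ = 0.3, 0.5, 0.7: factors 1.27, 1.75, 2.47; errors 8%, 14%, 21%. Simulation gives about 8%, 13 to 14% and 22%.
- k = 2 (the two products of one strength): factors 1.09, 1.25, 1.49; errors 6%, 8%, 11%. Simulation gives about 6 to 7%, 8% and 11 to 12%.

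**Step 4, after correction.** In the same simulations, the correlation within one product (n = 18) rejects in about 5% of trials. So does the correlation after removing product and subject means, tested on (18 − 1)(4 − 1) − 1 = 50 degrees of freedom.

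**The case against.** The strongest reply is that the protocol nowhere says the products are pooled. Proc corr can be run by product, section 17.1 presents summaries by treatment where applicable, and section 17 leaves detail to the SAP. This stands in part: pooling is an inference. It remains the natural reading, because one correlation is listed, covariate adjustment is excluded, and the neighbouring sentences of section 17.6 do specify per-pouch summaries, within-subject differences or summaries by treatment and period, while this one specifies nothing.

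A second reply is that the endpoint asks for a correlation, not a within-product one. If the stronger pouch gives both more extraction and more AUC, the two are truly associated overall, and finding that is not a false positive. This also stands. A reader might infer that the pooled test would be significant whatever the truth. It would not: the mixing effect depends on AUC rising with strength and vanishes if it does not. The problem is interpretation, since the pooled coefficient cannot separate the strength contrast from individual extraction.

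A reader might also infer that sections 8.2.1 and 17.6 contradict each other about snus. They do not. Section 17.6 leaves the ZYN restriction unrepeated and nowhere says that snus is included.

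Finally, this is one secondary endpoint without a success criterion, and section 17.7.3 warns against conclusions based solely on significance. That limits the consequence but does not make a pooled coefficient interpretable.

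**Conclusion.** The point holds conditionally. As written, the plan permits and most naturally implies a pooled correlation. If pooled, the coefficient largely reflects 3 versus 6 mg, and its p-value ignores repeated subjects.

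With no association within a product, p<0.05 occurs in about 42 to 100% of trials at AUC ratios of 1.5 to 2.0 and about 22 to 92% at 1.25, over the CV ranges above. Every setting is well above 5%. A reader might infer near-certain strong significance. That is true only at low to moderate variability: at the high-variability end, p<0.001 occurs in 30% of trials or fewer. None of the ZYN inputs is in the protocol.

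Repetition alone is the smaller problem. The errors of about 8%, 13 to 14% and 22% apply to four pairs per subject; within one strength they are about 6 to 7%, 8% and 11 to 12%.

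The primary AUCinf comparison is unaffected. The change is worth making because it costs almost nothing and the coefficient would otherwise be hard to interpret.

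**What to change.** In section 17.6, state that the correlation uses AUCinf and ZYN pouches only, matching section 8.2.1 item 3, and that it is reported separately for each of the four ZYN products (n = 18 each at most).

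If a combined estimate is wanted, it should account for product and subject. Options are a repeated-measures correlation, or a slope with 95% CI from a model with product and period as fixed effects and subject as random. Name these as design factors that section 17.7.1 does not cover, so that the model does not appear to breach the exclusion of covariate adjustment. The slope is a different quantity from a correlation and should be labelled as such.

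The cost is a sentence or two of text and a few lines of code, with no new data. The reported correlation will probably be smaller and, with 18 pairs per product, less precise.
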